7.8. Treatment after the End of the Study

7.8.1. Continued Access

LY900014 will not be made available after conclusion of the study to patients. Rapid-acting insulin analogs and regular human insulin are available in all countries for use as prandial insulin.

7.8.2. Special Treatment Considerations

After discontinuation of IP at the end of the treatment period or earlier, randomized patients should restart the prandial insulin used prior to study entry or transition to a rapid-acting insulin analog other than insulin lispro if the patient was not treated with insulin lispro prestudy. Patients may continue treatment with the basal insulin used during the study or return to their prestudy basal insulin at investigator discretion.

Please also refer to [Appendix 8](#) for information regarding the insulin lispro antibody follow-up assessment. During this follow-up period, OAMs used during the study treatment period should be continued and other prestudy OAMs may be considered at investigator discretion as appropriate.

Investigators should provide patients with appropriate guidance for glucose monitoring and insulin dose adjustment throughout the follow-up period in order to maintain glycemic control.

8. Discontinuation Criteria

8.1. Discontinuation from Study Treatment

In the event that the patient is discontinued from the study treatment, the investigator should encourage the patient to remain in the study for continued safety monitoring.

Lilly recognizes the importance of complete data collection. This study includes elements to minimize missing data. Randomized patients who are discontinued from IP before study completion are encouraged to remain in the study for continued monitoring. For patients who remain in the study after early discontinuation of IP, both efficacy (including HbA1c) and safety data will be collected at scheduled visits. The difference between stopping IP and discontinuing the study will be explained to patients as part of the informed consent, and patients will be encouraged to continue in the study even if they stop study drug. In addition, study site investigators will be trained on the importance of complete data collection, with additional re-education of sites and patients as necessary.

8.1.1. *Permanent Discontinuation from Study Treatment*

Patients will be discontinued from the IP in the following circumstances:

- The investigator may decide that the patient should stop IP. If this decision is made because of an AE, SAE, or a clinically significant laboratory value, the study drug is discontinued for that patient and appropriate measures are to be taken. Lilly or its designee is to be alerted.
- The patient may decide to stop IP.
- If the patient becomes pregnant.
- If an investigator, study site personnel performing assessments, or patient is unblinded, the patient must discontinue IP.
- If the patient, for any reason, requires treatment with another therapeutic regimen or therapeutic agent that has been demonstrated to be effective for treatment of the study indication. Discontinuation from IP should occur prior to introduction of the new agent.
- Use of prohibited concomitant medication, see [Table ITRN.8](#).
- If the patient has not taken IP for more than 14 consecutive days.

Discontinuation of the IP for abnormal liver tests **should be considered** by the investigator when a patient meets one of the following conditions after consultation with the Lilly designated medical monitor:

- ALT or AST >8X ULN.
- ALT or AST >5X ULN for more than 2 weeks.
- ALT or AST >3X ULN and TBL >2X ULN or prothrombin time >1.5X ULN.

- ALT or AST >3X ULN with the appearance of fatigue, nausea, vomiting, right upper-quadrant pain or tenderness, fever, rash, and/or eosinophilia (>5%).
- alkaline phosphatase (ALP) >3X ULN.
- ALP >2.5X ULN and TBL >2X ULN.
- ALP >2.5X ULN with the appearance of fatigue, nausea, vomiting, right upper-quadrant pain or tenderness, fever, rash, and/or eosinophilia (>5%).

8.1.2. Temporary Discontinuation from Study Treatment

During the study, patients who temporarily discontinue the IP may be able to resume IP based on the following scenario:

Patient has not taken IP for 14 consecutive days or less:

- If the treatment regimen restarts within 14 days of when the patient initially stopped taking IP, patient may continue in the study and begin treatment again with IP. During this time, nonstudy insulins may have been used. If the patient decides to continue in the study, no early termination procedures will be completed. Patients will continue study visits through the safety follow-up.

8.1.3. Discontinuation of Inadvertently Enrolled Patients

If the sponsor or investigator identifies a patient who did not meet enrollment criteria and was inadvertently enrolled, a discussion must occur between the Lilly CRP and the investigator to determine if the patient may continue in the study. If both agree it is medically appropriate to continue, the investigator must obtain documented approval from the Lilly CRP to allow the inadvertently enrolled patient to continue in the study with or without treatment with IP.

8.2. Discontinuation from the Study

Some possible reasons that may lead to permanent discontinuation include:

- Enrollment in any other clinical trial involving an IP or enrollment in any other type of medical research judged not to be scientifically or medically compatible with this study
- Participation in the study needs to be stopped for medical, safety, regulatory, or other reasons consistent with applicable laws, regulations, and good clinical practice (GCP)
- The investigator decides that the patient should be discontinued from the study
- The patient requests to be discontinued from the study
- The patient discontinues insulin lispro or study allowed basal insulin regimen for >14 consecutive days in the lead-in period.

Patients who discontinue the study early but after randomization will have early discontinuation procedures performed as shown in the Schedule of Activities (Section 2).

Patients who discontinue during the lead-in period will not need to fast, have laboratory samples drawn, or complete questionnaires, but will have all other early discontinuation procedures performed.

8.3. Lost to Follow-Up

A patient will be considered lost to follow-up if he or she repeatedly fails to return for scheduled visits and is unable to be contacted by the study site. Site personnel are expected to make diligent attempts to contact patients who fail to return for a scheduled visit or were otherwise unable to be followed up by the site.

9. Study Assessments and Procedures

Section 2 lists the Schedule of Activities, with the study procedures and their timing (including tolerance limits for timing).

Appendix 2 lists the laboratory tests that will be performed for this study.

Unless otherwise stated in the subsections below, all samples collected for specified laboratory tests will be destroyed within 60 days of receipt of confirmed test results. Certain samples may be retained for a longer period, if necessary, to comply with applicable laws, regulations, or laboratory certification standards.

9.1. Efficacy Assessments

9.1.1. Primary Efficacy Assessments

The primary efficacy measure is the change from baseline to Week 26 in HbA1c.

9.1.2. Secondary Efficacy Assessments

The following secondary efficacy measures will be collected at the times shown in the Schedule of Activities (Section 2).

- Fasting and PPG collected during the MMTT
 - 1-hour and 2-hour PPG excursions: serum glucose measured 1-hour and 2-hours after the start of a meal minus fasting serum glucose
 - Incremental areas under the serum glucose concentration-time curve from 0 to 30 minutes, 0 to 1 hour, 0 to 2 hours, 0 to 3 hours, and 0 to 4 hours after a meal; maximum serum glucose after a meal
 - Glucose variability measured by the coefficient of variation and standard deviation (SD)
- 1,5-Anhydroglucitol (1,5-AG)
- SMBG 10-point profiles (fasting, 1-hour post morning meal, 2-hours post morning meal, pre midday meal, 1-hour post midday meal, 2-hours post midday meal, pre evening meal, 1-hour post evening meal, 2-hours post evening meal, and bedtime)
 - 1-hour and 2-hour PPG excursions
 - Within- and between-day glucose variability measured by the coefficient of variation and SD
- Proportion of patients with HbA1c $\leq 6.5\%$ and $< 7.0\%$
- Prandial, basal, and total insulin dose (units and units/kg), and prandial/total insulin ratio.

9.1.3. Appropriateness of Assessments

All efficacy and safety assessments included in this study are generally regarded as reliable and accurate with respect to diabetes.

9.1.4. Study Procedures

The following procedures will be performed at the times shown in the Schedule of Activities (Section 2).

9.1.4.1. Electronic Clinical Outcomes Assessment

The eCOA diary will collect all glucose data directly from the BG meters, thereby increasing the validity of measures reported by the patient and minimizing transcription errors in recording the measures. The use of e-diaries should also allow more complete and accurate capturing of hypoglycemia events, as well as more frequent and timely interactions between investigator and patients as the intensity of their individual diabetes management increases. The system will be used to collect prandial insulin doses (date, time, and actual dose taken) and the basal insulin dose, on the 3 days prior to study visits, on the days of 10-point SMBG profiles, and at other times as clinically indicated. Hypoglycemic events will be captured throughout the clinical study in eCOA along with date and time of the BG level if measured and hypoglycemia treatment and outcome data. Additionally, the eCOA system will incorporate study-specific reminders for patients to perform the 10-point SMBG profiles.

Physicians and designated clinical staff will have access to the eCOA portal (secure web-based site) with the ongoing near real-time updating of BG readings, insulin doses administered, and hypoglycemic events. Manual inspection of data will support at least weekly patient monitoring as an enhancement to standard of care for patient safety, as well as the potential for reaching an optimum efficacy outcome. Investigative staff will assess clinical data via the eCOA portal and recommend adjustments in basal and prandial insulin (also refer to Section 7.2.1).

An instruction manual will be provided to patients and investigative sites. Additional instruction and training will be provided to the investigative sites regarding data collection, review, retention and archival processes. In the event of eCOA malfunction or loss, the patient will be instructed to immediately contact the investigative site for instructions regarding replacement of the equipment.

9.1.4.2. Four-Point Self-Monitoring Blood Glucose

Patients should be instructed to measure a minimum of 4 SMBG readings daily (consists of fasting [pre morning meal], pre midday meal, pre evening meal, and pre bedtime), with additional readings as needed for glucose self-management. Site personnel may request additional SMBG monitoring from patients and/or assess SMBG values at other times (such as postprandial SMBG readings) to make clinical management decisions. Missing values in 4-point SMBG profiles will not be considered protocol deviations unless, in the opinion of the investigator, they are excessive and reflect noncompliance with the protocol.

9.1.4.3. Ten-Point Self-Monitoring Blood Glucose

Patients in both study groups should be instructed to perform 10-point SMBG profiles prior to 5 visits during the study (Visits 8, 11, 13, 15, and 18). Three 10-point profiles should be done during the 2 weeks prior to each visit. Each 10-point profile during this 2-week time interval should be completed over a 1-day period, preferably on 3 nonconsecutive days (weekdays and weekends), as per the Schedule of Activities (Section 2). The 10-point profile consists of 10 SMBG measurements on the same day at premeal, 1-hour, and 2-hours after the start of the morning, midday, and evening meals, and at bedtime. The 10-point SMBG profile is inclusive of the daily 4-point SMBG readings. Patients should be encouraged to eat a morning, midday, and evening meal on the days that the 10-point SMBG is monitored. Premeal measurements should be taken before the patient begins eating the meal. Patients may eat a snack and cover with bolus insulin if that is their usual practice. Missing values in 10-point SMBG profiles will not be considered protocol deviations unless, in the opinion of the investigator, they are excessive and reflect noncompliance with the protocol.

9.1.4.4. Mixed-Meal Tolerance Test

A 4-hour MMTT will be performed in all patients at baseline (Week 0, Visit 8) and at the end of primary treatment period (Week 26, Visit 18). Patients will be instructed to fast for at least 8 hours prior to the administration of the MMTT at the study site. The MMTT can occur 0 to 4 days prior to the visit. The MMTT can be rescheduled up to 2 times within the visit window, ideally at 24-hour intervals, if the patient does not meet the target FBG. It is preferred for the rescheduled MMTT to occur as close to the visit date as possible.

Target FBG prior to the MMTT: Patients must have an FBG range of 71 to 180 mg/dL (3.9-10.0 mmol/L) prior to starting the MMTT. If the glucose is outside of this range, the MMTT should be rescheduled.

In order to increase the likelihood of having patients arrive the morning of the MMTT within the target FBG range, please note the following:

- Patients should be instructed to avoid major changes in dietary intake or physical activity during the 3 days prior to the MMTT.
- Patients should be instructed to inject basal insulin according to their usual schedule.
- Patients should not administer correction doses with insulin lispro or LY900014 within 4 hours of the start of the MMTT.
- During the 8-hour fasting period and up to 2 hours prior to the start of the MMTT, episodes of non-severe hypoglycemia (symptoms or BG \leq 70 mg/dL [3.9 mmol/L]) can be treated with 15 to 20 grams of carbohydrate. If a hypoglycemic episode requires more than approximately 20 grams of carbohydrate within 8 hours of the start of the MMTT or the patient experiences a severe hypoglycemic episode (as defined in Sections 9.4.1 and 9.4.2), the patient should be instructed to notify the site and the MMTT must be rescheduled.

Test Meal: The MMTT meal will consist of a standardized liquid nutrition shake(s) (such as Ensure Plus®, Abbott Nutrition). Patients are expected to consume the meal within 15 minutes.

Patients should consume the same test meal for both the baseline and end of primary treatment period MMTT, if possible.

Insulin Injection: During the Visit 8 MMTT, all patients will have insulin lispro injected 0 to 2 minutes before the start of the meal. During the Visit 18 MMTT, patients will have their blinded study insulin, either LY900014 or insulin lispro, injected 0 to 2 minutes before the start of the meal. The prandial insulin dose administered during the MMTT will be individualized for each patient.

- If the patient uses the carbohydrate counting prandial dosing plan, the morning meal insulin to carbohydrate ratio will be used to calculate the prandial insulin dose for the MMTT.
- If the patient does not use carbohydrate counting, the prandial insulin dose for the MMTT will be calculated based on the average total daily insulin dose for the 3 days prior to the MMTT per [Table ITRN.9](#).
- Modifications in the calculation of the insulin dose may also be influenced by other clinical circumstances and safety considerations known to the investigator; thus the MMTT prandial insulin dose is determined by, and the responsibility of, the investigator.

Table ITRN.9. Insulin to Carbohydrate Ratio for the MMTT Prandial Insulin Dose

Average Total (Basal+Bolus) Insulin Dose (units) in the Last 3 Days	Insulin to Carbohydrate Ratio (1 unit per number of grams carbohydrate)
8-11 units	1 unit : 50 grams
12-14	1:40
15-18	1:30
19-21	1:25
22-27	1:20
28-35	1:15
36-45	1:12
46-55	1:10
56-65	1:8
66-80	1:6
81-120	1:5
>120	1:4

Source: Scheiner [WWW].

Hypoglycemia during the MMTT: If the patient has signs or symptoms of hypoglycemia during the MMTT, BG should be measured with a glucometer. If the patient's BG is ≤ 70 mg/dL (3.9 mmol/L), the patient should receive 15 grams of rapidly absorbable carbohydrate. The patient's BG should be retested in 15 minutes or as clinically indicated and if remains ≤ 70 mg/dL (3.9 mmol/L), treatment with another 15 grams of carbohydrate should be given until BG is >70 mg/dL (3.9 mmol/L). Sample collection should continue per the schedule if possible.

Sample Collection: Time 0 of the MMTT will be when the patient starts to consume the meal. Serial venous blood samples to measure serum glucose will be taken at time -15, 0, 15, 30, 60, 120, 180, and 240 minutes after the start of the meal.

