Abbreviation: SMBG = self-monitored blood glucose.

^a Median SMBG value at target range OR experienced 1 unexplained hypoglycemic event (≤ 70 mg/dL [3.9 mmol/L]) or signs/ symptoms consistent with hypoglycemia noted.

Target Range: Premeal: 80 to <110 mg/dL (4.4 to 6.1 mmol/L)

Bedtime: 90 to 130 mg/dL (5.0 to 7.2 mmol/L)

1-2 hour postprandial: <140 mg/dL (7.8 mmol/L).

Source: Adapted from Bergenstal et al. 2008.

For either prandial insulin dosing plan, the investigator may determine the appropriate correction factor for the patient to administer when premeal SMBG are above target based on clinical judgment, taking into account the patient's clinical history with previous/current insulin regimen and recent glucose profiles. Alternatively, the correction factor may initially be calculated as follows:

correction factor = $1800/\text{total daily insulin dose}$ = estimated decrease in SMBG (mg/dL) level per unit of prandial insulin administered or

correction factor = $100/\text{total daily insulin dose}$ = estimated decrease in SMBG (mmol/L) level per unit of prandial insulin administered

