9.4. Safety

9.4.1. Hypoglycemia

Patients are encouraged to perform SMBG whenever hypoglycemia may be suspected, either by symptoms experienced or perceived increased risk as related to dietary intake, physical activity, or inadvertent or atypical insulin dosing. All patients will be instructed to treat a BG ≤ 70 mg/dL (3.9 mmol/L) as hypoglycemia.

Hypoglycemia events will be collected in eCOA (Section 9.1.4.1). If a hypoglycemia event is suspected, the patient should record the BG value, any associated symptoms, and the treatment administered in eCOA. The patient should contact the site as necessary. Reports of hypoglycemia will be classified by the investigator as “severe” or “not severe” based upon data collected in eCOA and in consultation with the patient, see below and Section 9.2.1. All episodes of severe hypoglycemia must be reported as AEs via electronic data entry, and as SAEs.

Hypoglycemia will be described using the following definitions:

- **Documented hypoglycemia**
 - **Documented symptomatic hypoglycemia:** an event during which typical symptoms of hypoglycemia are accompanied by BG of ≤ 70 mg/dL (3.9 mmol/L);
 - **Documented asymptomatic hypoglycemia:** an event not accompanied by typical symptoms of hypoglycemia but with a BG concentration of ≤ 70 mg/dL (3.9 mmol/L);
 - **Documented unspecified hypoglycemia:** an event during which BG ≤ 70 mg/dL (3.9 mmol/L) but no information relative to symptoms of hypoglycemia were recorded;
- **Probable symptomatic hypoglycemia:** an event during which symptoms are indicative of hypoglycemia and which was presumably caused by BG ≤ 70 mg/dL (3.9 mmol/L) although no BG measurement was reported;
- **Severe hypoglycemia:** An event requiring assistance of another person to actively administer carbohydrate, glucagon, or other resuscitative actions. During these episodes, the patient has an altered mental status and cannot assist in his/her own care, may be semiconscious or unconscious, or experience coma with or without seizures, and may require parenteral therapy. BG measurements may not be available during such an event, but neurological recovery attributable to the restoration of BG concentration to normal is considered sufficient evidence that the event was induced by a low BG concentration (BG ≤ 70 mg/dL [3.9 mmol/L]).

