The definitions of baseline and post-baseline for the efficacy and safety analyses depend on which analysis period is being used. The following analysis periods will be used:

- Lead-in Period – Visits 2 to 8
- 26-Week Treatment Period – from randomization to Week 26 prior to discontinuation of IP and from randomization to Week 26 (including all data regardless of IP use)
- 26-Week Treatment Period and Safety Follow-Up Visit – from randomization to Visit 801 (including all data regardless of IP use)

The data on IP is defined based on the following rules:

- For data only measured at an office visit
 - MMTT postbaseline data will be classified as on IP if the MMTT performance date is prior to or on the last IP dose date
 - Other postbaseline data (for example, vital signs, safety laboratory tests, and questionnaires) will be considered as on IP if the measurement was performed at or prior to the cutoff date defined as 14 days after the last IP dose date
- For data collected as running records with an exact date stamp such as adverse events (AEs) and diary entries where the dates of the measures were not tied with the date of an office visit, postbaseline data with dates \leq (last study drug dose date +1) will be considered as data on IP.

Table 6.2 describes the rules for determining the patient population, baseline and postbaseline observations for the different analysis periods.

For continuous measures, summary statistics will include sample size, mean, SD, median, minimum, and maximum for both the actual and the change from baseline measurements. Least-squares (LS) means and standard errors derived from the analysis models will also be displayed. Treatment comparisons will be displayed showing the treatment difference LS means and the 95% CIs for the treatment differences, along with the p-values for the treatment comparisons.

For categorical measures, summary statistics will include sample size, frequency, and percentages. Fisher's exact test or Pearson's chi-square test will be used for treatment comparisons.

For laboratory values, both conventional (CN) and Systeme International (SI) units will be presented. Therefore, both % and mmol/mol will be presented for HbA1c and both mg/dL and mmol/L will be presented for glucose measurements.

All baseline measures will be analyzed using an analysis of variance (ANOVA) model that has treatment as the model term.

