6.12.4.1. Hypoglycemic Events

Hypoglycemia events that occur during the study outside the MMTT will be captured using an eCOA diary starting from Visit 2 through Visit 801. Whenever hypoglycemia is suspected, the patient should record the blood glucose value, any associated symptoms, and the treatment administered in eCOA. A set of events is counted as 1 event in analysis if it consists of an originating event and subsequent continuing events as marked by the patient in eCOA, or the duration between adjacent events is ≤ 30 minutes. The event with the highest severity will be selected for analysis with severity determined in the order of: 1) it is a severe hypoglycemia, 2) it has symptoms of hypoglycemia reported, and 3) it has the lowest blood glucose value. If there are multiple events tied in all 3 aspects, the event with the largest number of non-missing responses to the questions of nocturnal hypoglycemia and postmeal time frame will be selected. If there are still multiple events tied, the latest event (based on data entry time) will be selected.

The following types of hypoglycemia events will be derived in the analysis data sets: documented hypoglycemia, severe hypoglycemia, nocturnal hypoglycemia, probable symptomatic hypoglycemia, and overall hypoglycemia. Only severe hypoglycemia will be collected as AEs and all episodes of severe hypoglycemia will be considered as SAEs. Documented hypoglycemia (including documented symptomatic hypoglycemia, documented asymptomatic hypoglycemia and documented unspecified hypoglycemia) will be based on blood glucose (BG) ≤ 70 mg/dL. In addition, documented clinically significant hypoglycemia with similar criterion as above documented hypoglycemia except for the threshold of BG < 54 mg/dL will be summarized.

Table 6.6 provides detailed statistical methods for each endpoint related to hypoglycemia. For these analyses, hypoglycemia events prior to the discontinuation of IP will be summarized.

Additional analyses for other types of hypoglycemic events not mentioned in the table and for the post-treatment period may be conducted as needed.

The incidence and number of episodes of hypoglycemia during the MMTT will be summarized by treatment and time relative to the meal (≤ 0.5 , ≤ 1 , ≤ 2 , ≤ 4 , >1 to ≤ 2 and >2 to ≤ 4 hours after start of the meal) and analyzed by Fisher's exact test.

A listing of patients with at least 1 severe hypoglycemia reported (as SAE) after randomization will be provided.

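### A displayed 3.9 mmol/L both permits the mixed-meal test to start and counts as hypoglycemia to be treated, because 71 and 70 mg/dL are printed as the same mmol/L value

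*Protocol*

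**What the plan says.** **Starting the test.** Protocol 9.1.4.4 sets the entry condition: "Patients must have an FBG range of 71 to 180 mg/dL (3.9-10.0 mmol/L) prior to starting the MMTT". The lower end is included, since only values beyond the range lead to postponement: "If the glucose is outside of this range, the MMTT should be rescheduled". Insulin is part of the test: "During the Visit 8 MMTT, all patients will have insulin lispro injected 0 to 2 minutes before the start of the meal". At Visit 18 the blinded study insulin is given with the same timing.

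**Hypoglycemia.** Protocol 9.4.1 has all patients treat a reading at or below "70 mg/dL (3.9 mmol/L) as hypoglycemia". The same pair, 70 mg/dL with 3.9 mmol/L in brackets, recurs in the event definitions of 9.4.1. It also recurs in 9.1.4.4, for episodes during the fast and during the test.

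**Analysis.** SAP 6.12.4.1 and the footnote to Table 6.6 define documented hypoglycemia by 70 mg/dL or below, with no mmol/L figure. SAP 6.1 says that "both mg/dL and mmol/L will be presented for glucose measurements", in a paragraph about laboratory values. The SAP gives no conversion factor, rounding rule or governing unit for meter readings. Protocol 9.1.4.1 says glucose data come directly from the meters but does not name their unit.

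**The concern.** In mg/dL the plan is consistent: 71 or above may start, 70 or below is hypoglycemia. In mmol/L to one decimal, 3.9 is the lowest value that may start and also the highest value that is hypoglycemia. The protocol gives its limits in both units, so the mmol/L figures appear to be meant for use.

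What is at stake is a safety decision. One section lets prandial insulin be injected at a reading that another section says to treat. Nothing in 9.1.4.4 says which instruction prevails when the 3.9 is found at the check before the test. Two sites could act differently on the same display and each be following the protocol.

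There is a lesser, separate matter in the SAP. Without a conversion and rounding rule, the programmer decides whether a 3.9 recorded in mmol/L is an event.

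**Working it through.** **Inputs**
- MMTT start range: 71 to 180 mg/dL, printed 3.9-10.0 mmol/L (Protocol 9.1.4.4).
- Hypoglycemia: 70 mg/dL or below, printed 3.9 mmol/L (Protocol 9.4.1 and 9.1.4.4).
- Conversion factor f: Protocol 7.2.1.4 gives the correction factor as 1800/total daily dose in mg/dL and 100/total daily dose for the "estimated decrease in SMBG (mmol/L) level per unit of prandial insulin administered". So f = 1800/100 = 18.
- Check on f: eleven glucose pairs printed in the protocol (for example 90 and 5.0, 100 and 5.6, 180 and 10.0) are all reproduced by factors from about 17.99 to 18.018.

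**Step 1. Reproduce the printed limits.** mmol/L = (mg/dL)/f.
- 71/18 = 3.94, prints as 3.9.
- 70/18 = 3.89, prints as 3.9.

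Both figures are correctly rounded. The overlap arises because two adjacent mg/dL values share one displayed mmol/L value.

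**Step 2. What a displayed 3.9 covers.** The rounding interval is 3.85 to 3.95 mmol/L.
- 3.85 × 18 = 69.3 mg/dL.
- 3.95 × 18 = 71.1 mg/dL.

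The display spans the boundary and cannot separate 70 from 71.

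**Step 3. How the protocol handles the same problem elsewhere.** In Table ITRN.5, 109/18 = 6.06 and 110/18 = 6.11 both round to 6.1. That table prints the adjoining bands as 4.4-6.1 and >6.1-7.2, so 6.1 falls in one band only. Section 9.1.4.4 has no such bound.

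**Step 4. How many tests.** The documents give no fasting glucose distribution for the MMTT. Assume it is roughly normal and take the probability of 69.3 to 71.1 mg/dL:

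| Assumed mean, SD (mg/dL) | Share of tests displaying 3.9 |
|---|---|
| 100, 20 | 1.2% |
| 110, 25 | 0.8% |
| 120, 30 | 0.6% |
| 130, 35 | 0.5% |

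If every site worked in mmol/L, which overstates the matter:
- Week 26, 568 completers: 0.005 × 568 = 2.8 to 0.012 × 568 = 6.8, about 3 to 7 tests.
- Baseline and Week 26, 670 + 568 = 1,238: 0.005 × 1,238 = 6.2 to 0.012 × 1,238 = 14.9, about 6 to 15 tests.

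**Step 5. The SAP threshold.** 3.9 × 18 = 70.2 mg/dL (70.16 at f = 17.99; 70.27 at f = 18.018).
- Unrounded: 70.2 > 70, not an event.
- Rounded to whole mg/dL: 70, an event.

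An unrounded result of 70 or below would need f ≤ 70/3.9 = 17.949, outside the range the printed pairs allow. The classification therefore depends on a rounding rule that the SAP does not state.

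**The case against.** **It is only rounding.** Every limit is written in mg/dL first, with mmol/L in brackets. Section 9.4.1 even prints both at-or-below 70 and above 70 mg/dL with 3.9 mmol/L, so the bracket reads as a translation of the cut-off. This is right about the cause. It does not help a site whose display reads 3.9, because nothing says that mg/dL governs and the mg/dL value cannot be recovered from the display.

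**The safety exposure is limited.** The test is done at the study site and the meal follows injection within 2 minutes. The investigator determines the dose, and glucometer checks and carbohydrate rescue are specified. The rule for hypoglycemia during the test applies when the patient has signs or symptoms, so a 3.9 before the test does not by itself trigger it. All of this stands and limits the consequence. The conflict between the start rule and 9.4.1 remains.

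**The excursion endpoints hardly move.** This stands. A displayed 3.9 lies at most 71 − 69.3 = 1.7 mg/dL below the permitted 71, and its upper part (70.5 to 71.1) rounds to 71, which is eligible in mg/dL. Excursions are computed from venous serum glucose, and SAP 6.11.5 averages the -15 and 0 minute samples for the fasting value. A reader might infer that the 1-hour and 2-hour comparisons start from hypoglycemic baselines to a degree that matters; the documents do not support that.

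**The SAP does not redefine the event.** A reader might infer that the SAP excludes every 3.9 mmol/L reading, so that a sizeable share of events from mmol/L meters is lost. That needs three conditions: meters recording in mmol/L, conversion to mg/dL, and no rounding. Neither document states any of them. The SAP keeps the protocol's 70 mg/dL threshold, and with rounding to the precision of that threshold 3.9 is an event. The documents also give no distribution of low readings from which to size a loss. Treatment is double-blind and randomization is stratified by country, so no bias between arms is shown. Objectives 6 and 7 lie outside the multiplicity procedure.

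**Conclusion.** The contradiction between Protocol 9.1.4.4 and 9.4.1 is real. It follows from the printed limits and one-decimal rounding, for any site that reads glucose in mmol/L. It is confined to one displayed value and does not exist at sites working in mg/dL. Under the assumed normal distributions it touches about 0.5% to 1.2% of MMTTs at mmol/L sites; the documents do not say which sites those are. The HbA1c primary analysis and its power do not involve these readings, and the excursion endpoints are not materially affected. It merits correction because it sits at a decision about giving insulin, not because of its statistical weight.

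The SAP matter is missing detail rather than an error. A 3.9 mmol/L reading is an event or not according to an unstated rounding rule. If left unrounded, a symptomatic 3.9 would fit the category of relative hypoglycemia in Protocol 9.4.1, which is excluded from overall hypoglycemia. That remains conditional on how readings are stored and converted.

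**What to change.** **Protocol.** Reconcile the mmol/L limits in 9.1.4.4 and 9.4.1 so that no displayed value both permits the MMTT to start and is hypoglycemia to be treated. Which limit applies is a clinical decision for the sponsor. Whatever is chosen, the explicit inequality signs in Table ITRN.5 show a notation that avoids the overlap. The cost is a clarification letter or a one-line amendment.

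**SAP.** In 6.12.4.1 and Table 6.6, state the governing unit for the 70 mg/dL threshold, the conversion factor and the rounding. The choice should be explicit, because classifying in the meter's own unit does not by itself give one definition. A displayed 3.9 mmol/L reaches about 71.1 mg/dL, while a whole-number display of 70 mg/dL reaches about 70.5. The cost is one sentence, settled before unblinding. No new data are needed.
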